- A. Obtain information by intervening or interacting with living individuals for research purposes*
- B. Obtaining identifiable private information about living individuals*
- C. Obtaining the voluntary informed consent of individuals to be subjects*
- D. Makes decisions about subject eligibility*
- E. Studying, interpreting, or analyzing identifiable private information or data/specimens for research purposes*
- F. Studying, interpreting, or analyzing de-identified data or specimens for research purposes*
- G. Some/all research activities performed outside NIH*

Investigational Agents:

Drug Name:	[¹⁸ F] Fluoromisonidazole, 1 H-(3-[¹⁸ F]-fluro-2-hydroxyl-propyl)-2-nitro-imidazole, [¹⁸ F] FMISO
IND Number:	124706
Sponsor:	[name]
Manufacturer:	Cardinal Health

Abbreviated Title: [¹⁸F]-FMISO Imaging Post TACE

Version Date: 08/31/2016

PRÉCIS

Background

- TACE is the standard therapy for inoperable primary liver cancers or tumor control prior to transplantation. The mechanisms for TACE's failure remains poorly understood.
- Although acute hypoxia and significant tumor necrosis occurs following TACE, the tumor adaptive response and localization for such have not been well characterized.
- Imaging tools using a hypoxia-specific tracer [¹⁸F] FMISO may help identify the pattern and distribution of acute post-TACE tumor hypoxia relative to demonstrated tumor progression.
- The primary hypothesis of this study states that tumor progression post-TACE arises from changes in tumor phenotype induced by treatment-related hypoxia superimposed on the dynamic process of underlying tumor hypoxia.

Objectives

To determine the feasibility of hypoxic tumor identification despite relatively high liver background signal, and describe patterns of tumor hypoxia in the immediate post-TACE treatment period using PET imaging [¹⁸F] MISO uptake registered with cross-sectional imaging.

Eligibility

- Patients ≥18 years of age with inoperable primary hepatic malignancy or hepatic-dominant metastatic disease and be otherwise eligible to receive TACE treatment. Patients with hepatocellular carcinoma should have intermediate stage disease according to the BCLC staging system (Stage A4 or B).
- Patients must not have had chemotherapy or radiation therapy to liver for at least 2 weeks prior to starting study treatments.
- Patients must not have an acute, critical illness.
- Patients must not be pregnant
- Able to understand and be willing to sign a written informed consent

Design

1 INTRODUCTION

1.1 STUDY OBJECTIVES

1.1.1 Primary Objective

To determine the feasibility of hypoxic tumor identification despite relatively high liver background signal, and describe patterns of tumor hypoxia in the immediate post-TACE treatment period using PET imaging [¹⁸F] MISO uptake registered with cross-sectional imaging.

1.2 BACKGROUND AND RATIONALE

1.2.1 Hypoxia and the Tumor Microenvironment

Hepatocellular carcinoma (HCC) is the sixth most common cancer across the globe and it represents the third most common cause of cancer related deaths. HCC represents 90% of primary liver cancers. Liver tumor resection or liver transplantation, are first-line treatment options for HCC. Patients who are neither a candidate for surgery or transplantation can undergo minimally invasive procedures such as local ablation or chemoembolization. Often there is tumor progression despite these treatments¹. The implications of tumor hypoxia following chemoembolization are unclear, although an association between hypoxia and more aggressive tumor phenotype is well known. As early as 1955, Thomlinson and Gray hypothesized that the presence of hypoxia may render lung cancers resistant to radiotherapy¹. Tumor hypoxia occurs when oxygen consumption is out of balance with supply, as with reduced perfusion or diffusion-limited oxygen delivery. Clinically relevant hypoxia is detected in approximately 50% of all solid tumors irrespective of their size and histological features².

Durand and Aquino-Parsons³ studied tumor perfusion in a human xenograft tumor model and observed varying degrees of overlap of fluorescent staining or changes in fluorescence intensity corresponding to significant variations in tumor perfusion over relatively short periods of time. More recently more complex mechanisms resulting in significant fluctuations in red cell flux and tumor oxygenation have been implicated as potential determinants of tumor radio-resistance and chemo-resistance^{4,5}. These fluctuations in tumor oxygenation may occur in cycles of extremely variable duration, on the order of minutes to hours, depending upon tumor type; various studies using different models have determined cycle durations of less than 2 cycles/minute⁶, cycles every 20-30minutes⁷ or 12 hours in patients imaged with PET hypoxia agents^{8,9} tumor hypoxia and TACE therapy of liver tumors.

TACE (transarterial chemoembolization) consists of the local transcatheter intrahepatic arterial delivery of chemotherapeutic agents combined with temporary occlusion of the artery(s) supplying the targeted neoplasm(s). The combination of acute ischemia and high concentrations of chemotherapeutic agent results in significant tumor necrosis, although the exact contribution of each mechanism remains poorly understood. Although TACE is considered palliative therapy for hepatic malignancy, TACE has been shown to prolong survival in patients with unresectable hepatocellular carcinoma (HCC) and is considered the standard of care for patients with unresectable intermediate HCC¹⁰. The treatment has also been shown to have a measurable and statistically significant decrease in the size of treated lesions in metastatic liver disease¹¹. The most common adverse effect of TACE is post-embolization syndrome, consisting of transient abdominal pain, nausea, vomiting, fever, and fatigue. Despite worldwide use of TACE for

unresectable HCC as well as chemo-refractory hepatic metastatic disease, TACE treatment failure is poorly understood. Several factors may play a role in tumor progression despite TACE, including tumor resistance to chemotherapeutic drugs, which may be enhanced by hypoxia.

Hepatic arterial embolization has been shown to yield discrete reductions in tumor perfusion in a liver tumor model using TRIP MRI imaging¹². In the same tumor model, embolization with 40-120µm microspheres was found to result in increased HIF-1a (hypoxia-inducible factor 1a) stabilization¹³. These results confirm the degree and effect of acute embolization-related hypoxia, which represents a unique subset in the spectrum of the hypoxic tumor microenvironment; acute severe hypoxia is superimposed upon portions of normoxic and cycling hypoxic tumor by virtue of proximal occlusion of the arterial supply of the tumor(s). Tumor tissue either undergoes ischemic necrosis or adaption to the acute hypoxic environment through hypoxia-induced gene expression and subsequent proliferation.

1.2.2 [¹⁸F]-FMISO

[¹⁸F] Fluoromisonidazole, 1 H-(3-[¹⁸F]-fluoro-2-hydroxyl-propyl)-2-nitro-imidazole, [¹⁸F] FMISO is an investigational PET radiopharmaceutical for injection and intended for use as tumor hypoxia imaging agent. [¹⁸F] FMISO possesses desirable qualities for evaluating hypoxia including an ideal partition coefficient and a relatively low required dose ($\leq 10\text{mCi}$). [¹⁸F] FMISO is reduced only in hypoxic tissues, resulting in hypoxia-specific intracellular accumulation.¹⁴ Imaging studies of head and neck as well as pancreatic tumor hypoxia using [¹⁸F] FMISO have been previously published¹⁵. This agent has shown no toxicity among 600 patients who received at least four administrations.

1.2.3 Rationale

The primary hypothesis of this study states that tumor progression post-TACE results from changes in tumor phenotype induced by sublethal treatment-related hypoxia. The goal of the proposed pilot study is to test the feasibility of hypoxia imaging of the liver post-TACE. Early imaging detection of residual hypoxic tumor acutely following TACE may ultimately correspond to undertreated tumor and could be used to optimize TACE outcomes with targeted combinational therapies.

This pilot study will evaluate fifteen patients who will receive TACE therapy for primary or metastatic hepatic malignancy. They will undergo PET imaging of the liver with [¹⁸F] FMISO to: 1) determine the feasibility of hypoxic tumor identification despite relatively high liver background signal, and 2) identify the pattern and distribution of acute post-TACE tumor hypoxia relative to demonstrated tumor progression despite therapy. Patients will be followed according to standard community practice with conventional cross-sectional imaging (CT and/or MRI) to confirm tumor progression. Image fusion analysis will be performed to determine degree of correlation between focal hypoxia and site(s) of progression.

2 ELIGIBILITY ASSESSMENT AND ENROLLMENT

2.1 ELIGIBILITY CRITERIA

2.1.1 Inclusion Criteria

- 2.1.1.1 Patients must have confirmed inoperable primary hepatic malignancy or hepatic dominant metastatic neoplastic disease evidenced by histology or cytology, or characteristic enhancement pattern on CT or MRI together with an abnormal serum alpha-fetoprotein >200mg/dl in the case of hepatocellular carcinoma.
- 2.1.1.2 Patients with hepatocellular carcinoma should conform to intermediate stage disease according to the BCLC¹⁶ staging system (Stage A4 or B) and be otherwise eligible to receive TACE treatment¹⁷.
- 2.1.1.3 Patients must have had no chemotherapy or radiotherapy to the liver for their malignancy for at least 2 weeks (or until response can be adequately assessed) prior to treatment and must have recovered from all clinically significant side effects of therapeutic and diagnostic interventions.
- 2.1.1.4 Serum creatinine less than or equal to 2.0 mg/dl unless the measured creatinine clearance is greater than 60ml/min
- 2.1.1.5 Age \geq 18 years
- 2.1.1.6 Ability of subject to understand and willingness to sign a written informed consent document
- 2.1.1.7 Patient must be able to lie still for the procedure
- 2.1.1.8 ECOG status \leq 2
- 2.1.1.9 In addition, for patients receiving TACE outside NIH:
 - Patient must have physician willing to collaborate with NIH PI by providing required medical record and digital MR/ CT scan documentation pre and post TACE procedure.
 - Patient must be willing to sign an Authorization for the Release of Medical Information form.
- 2.1.2 Exclusion Criteria
 - 2.1.2.1 Patients who have received prior TACE treatment
 - 2.1.2.2 History of allergic reactions attributed to compounds of similar chemical or biologic composition to misonidazole or other agents used in study.
 - 2.1.2.3 Patients with known brain metastases should be excluded from this clinical trial because of their poor prognosis and because they often develop progressive neurologic dysfunction that would confound the evaluation of neurologic and other adverse events.
 - 2.1.2.4 Uncontrolled intercurrent illness including, but not limited to ongoing or active infection, symptomatic congestive heart failure, unstable angina pectoris, cardiac

arrhythmia, or psychiatric illness/social situations that would limit compliance with study requirements.

2.1.2.5 Patients of childbearing age must not be pregnant. The effects of [¹⁸F] FMISO on the developing human fetus are unknown. Pregnancy is a contraindication for TACE.

2.1.3 Recruitment Strategies

Investigators will work closely to identify patients with colleagues at the NCI and in the local community including tumor board meetings to enlist their assistance in referrals.

2.2 SCREENING EVALUATION

Patients may have TACE either at the NIH or the institution of their choice.

The study procedure on this protocol is the FMISO scan, which will be performed at the NIH ONLY. An eligibility checklist will be completed by the Principal Investigator during initial contact. An eligibility checklist including inclusion/exclusion criteria will be completed by referring physician for patients treated with TACE outside NIH or the Principal Investigator for patients treated with TACE at NIH. Referring physicians will fax or email a completed checklist at least one week prior to TACE. Following the Principal Investigator's review of the returned checklist and confirmation of eligibility, patients will be contacted by a research staff member to 1) discuss the study and answer questions, and 2) to offer enrollment into the protocol and schedule an appointment(s) for [¹⁸F] FMISO PET-CT scanning.

The eligibility checklist will be reviewed with the patient when the patient provides informed consent and undergoes FMISO imaging. The consent process is described in section 9.4 and may occur over the telephone and by mail.

2.3 REGISTRATION PROCEDURES

The Principal Investigator, along with key research personnel, will screen and enroll all eligible patients on the study. The screening and enrollment process will be documented in CRIS. All patients enrolled in the study will receive a unique patient identifier and will be entered in the study's screening and enrollment logs which are kept in our research database. The study research database will be maintained in an electronic folder in a larger central shared drive with a secure password and Clinical Center network back-up, in accordance with NIH CC policy.

2.4 BASELINE EVALUATION

No specific pre-procedure laboratory studies are required prior to FMISO administration. Pre-TACE standard of care evaluation commonly occurs no more than four weeks prior to TACE and includes laboratory and imaging studies. These may include but not limited to:

- Baseline CT and MRI of the abdomen
- Tumor measurements
- Baseline laboratories including an acute care, hepatic, and mineral panel, PT, aPTT, INR, CBC with differential, and AFP at outside institution.
- Baseline history and physical exam
- B-hCG (Urine or Serum) will be performed within 48 hours of FMISO imaging

3 STUDY IMPLEMENTATION

3.1 STUDY DESIGN

Fifteen patients with metastatic or primary hepatic malignancy will be enrolled to yield a minimum of ten evaluable patients. Prior to TACE, all patients will undergo conventional baseline imaging. The first five patients enrolled will receive a single dose of the study imaging agent (FMISO) post-TACE to determine imaging parameters and feasibility. Subsequent to the feasibility study, the remaining patients (#6-15) will receive the hypoxia imaging agent before and following TACE to determine changes in uptake pattern attributable to arterial embolization. Following TACE patients will be monitored according to standard of care until tumor progression is documented. Registration of functional and/or metabolic imaging demonstrating progression with immediate post-TACE hypoxia imaging will be performed for correlative analysis.

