6 DATA COLLECTION AND EVALUATION

6.1 DATA COLLECTION

Data collection for this study will include imaging data used to identify acute post-embolization tumor hypoxia, as well as conventional post-treatment imaging and measurement of tumor markers used to identify tumor progression despite therapy. Other follow up data such as date of death will also be collected. The [¹⁸F] FMISO PET-CT imaging and post-treatment CT and MRI will be stored in PACS prior to image registration and analysis. PET-CT and conventional CT images will be transferred to a workstation for registration analysis. Identifiers will be removed from fused images for characterization of degree of overlap between documented tumor progression and acute post-treatment hypoxia. Imaging data including determination of response by mRECIST criteria as well as tumor marker levels will be collected in an Excel spreadsheet that will be stored in a password-protected PC kept in a secured office.

Grade 2 events and higher will be recorded in the study database. Grade 1 events will not be recorded or reported.

The PI will be responsible for overseeing entry of data into an in-house password protected electronic system and ensuring data accuracy, consistency and timeliness. The principal investigator, associate investigators/research nurses and/or a contracted data manager will assist with the data management efforts. Source data obtained during the conduct of the protocol will be kept in secure network drives or in approved alternative sites that comply with NIH security standards. Primary and final analyzed data will have identifiers so that research data can be attributed to an individual human subject participant.

End of study procedures: Data will be stored according to HHS and FDA regulations as applicable.

Loss or destruction of data: Should we become aware that a major breach in our plan to protect subject confidentiality and trial data has occurred, the IRB will be notified.

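### The progression mapping is planned against post-TACE FMISO uptake only, so it cannot tell uptake already present before TACE from uptake that is new after it, although patients 6-15 have both scans

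*Combined protocol and SAP*

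**What the plan says.** **Hypothesis.** Section 1.2.3 attributes progression after TACE to "changes in tumor phenotype induced by sublethal treatment-related hypoxia". The Précis words it as "treatment-related hypoxia superimposed on the dynamic process of underlying tumor hypoxia". The protocol thus recognizes two components of tumor hypoxia.

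**Scans.** Section 3.1 has two stages. For the first: "The first five patients enrolled will receive a single dose of the study imaging agent (FMISO) post-TACE to determine imaging parameters and feasibility". For the second: "the remaining patients (#6-15) will receive the hypoxia imaging agent before and following TACE to determine changes in uptake pattern attributable to arterial embolization". Section 3.4 allows the pre-TACE scan up to one week before TACE and puts the post-TACE scan at 24 to 72 hours.

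**Mapping to progression.** Section 3.1 plans: "Registration of functional and/or metabolic imaging demonstrating progression with immediate post-TACE hypoxia imaging will be performed for correlative analysis". Section 6.1 describes the measure as the "degree of overlap between documented tumor progression and acute post-treatment hypoxia". The Précis (Design) and the second aim in Section 1.2.3 also pair progression with acute hypoxia after TACE. Section 3.3 describes registering the progression CT or MRI to FMISO PET-CT without saying whether that is the pre-TACE scan, the post-TACE scan or both. Section 6.2.3 is equally unspecific.

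**Use of the pre-TACE scan.** Section 3.3 gives it one use: a descriptive before/after comparison, with change in peak SUV read as the response to embolization. Nothing there connects that comparison to the site of progression.

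**The concern.** The hypothesis concerns hypoxia produced by the treatment. Overlap between progression and post-TACE uptake would be seen if TACE-induced hypoxia led to progression. It would also be seen if tumor that was hypoxic all along was simply more likely to progress. A map built on the post-TACE scan alone looks the same in both cases.

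For patients 6-15 the trial acquires the scan that could help separate these explanations, and the patients accept its radiation, yet no planned step brings it into the progression analysis. The interpretation of the correlative result is at stake. Whether FMISO uptake can be seen in liver tumors after TACE is not.

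**Working it through.** The plan gives no power, alpha or effect-size figure on this point (Section 8 says such calculations do not apply), so there is no figure to reproduce. The check compares the sections and counts patients.

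**Step 1. Which scan is compared with progression?**

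| Section | FMISO scan set against progression |
|---|---|
| Précis, Design | Post-TACE |
| 1.2.3, second aim | Post-TACE |
| 3.1 | Post-TACE |
| 6.1 | Post-treatment |
| 3.3 | Not specified |
| 6.2.3 | Not specified |

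Every section that names the scan names the post-TACE one. None plans registration to the pre-TACE scan.

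**Step 2. Can the before/after comparison in Section 3.3 fill the gap?** No. Change in peak SUV is a difference between two maxima. It does not show where in the tumor uptake is new, and the two maxima need not lie in the same place or in the part that later progresses. Section 3.3 also looks for increased or decreased uptake near progression, but it does not define this as a change from the pre-TACE scan. Where the section explains increased uptake, the reference is background liver.

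**Step 3. What does the mapping lose?** A progression site can show four patterns:

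| Uptake before TACE | Uptake after TACE | Post-TACE map alone | Map using both scans |
|---|---|---|---|
| No | Yes | Uptake | New |
| Yes | Yes | Uptake | Persisting |
| Yes | No | No uptake | Lost |
| No | No | No uptake | None |

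Four patterns collapse to two. The pair that matters most for the hypothesis, new and persisting, becomes one.

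**Step 4. How many patients could be classified?** Section 3.1 states: "Fifteen patients with metastatic or primary hepatic malignancy will be enrolled to yield a minimum of ten evaluable patients".

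- Paired scans: 15 − 5 = 10 patients at most.
- Post-TACE scan only: 5/15 = 33%.
- If exactly 10 patients are evaluable, at least 10 − 5 = 5 and at most 10 come from patients 6-15. The number with usable pairs could be lower still, because the evaluability rule in Section 6.2.1.2 does not require a pre-TACE FMISO scan.
- The number of progression sites is not given and cannot be derived.

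**The case against.** The best defense is that this is a feasibility pilot. The only objective in Section 1.1.1 is feasibility and a description of hypoxia patterns after TACE. The second aim in Section 1.2.3 asks about post-TACE hypoxia, and post-TACE registration matches it. The practical rationale in 1.2.3, that residual hypoxic tumor may mark undertreated tumor, does not depend on when the hypoxia arose. All of this stands, and it confines the point to the correlative analysis. It does not remove the point, because that analysis appears in the design, image-analysis and data-collection sections and is introduced by a hypothesis about treatment-related hypoxia.

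Section 3.3 could also be read as allowing either scan. That is fair: it does not exclude the pre-TACE scan. It does not plan its use either.

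A third objection is that a pre-TACE scan is an imperfect baseline. Section 1.2.1 describes oxygenation cycling over minutes to 12 hours, and the scan may be a week old. Moreover, the Précis and Section 1.2.1 superimpose TACE hypoxia on hypoxia already there, so a site with uptake on both scans may still carry a treatment effect. This also stands. It means that statements about treatment-related hypoxia should not rest on newly positive sites alone, and the limits belong in the plan. An imperfect baseline is still more informative than none.

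Two stronger readings are tempting. A reader might infer that the plan counts pre-existing hypoxia as treatment-related. No section does so: mapped uptake is always named by its timing, and there is no rule assigning a cause. A reader might also infer that patients 1-5 are pooled with the rest in the mapping. No pooled estimate is specified, and Section 3.3 characterizes tumors individually.

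**Conclusion.** The point holds in a limited form. As planned, the progression mapping cannot distinguish uptake present before TACE from uptake new after TACE. Overlap with progression would therefore bear only weakly on the treatment-related-hypoxia hypothesis. The feasibility objective is unaffected.

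In patient numbers, the distinction could be added for at most 10 of 15 patients and never for the first 5. This assumes enrollment and scanning run as Section 3.1 describes.

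No size can be given in progression sites. Section 1.2.1 says "Clinically relevant hypoxia is detected in approximately 50% of all solid tumors", and a reader might infer that about half of the progression sites with post-TACE uptake were hypoxic beforehand. The documents do not support that step. The figure describes solid tumors in general. The quantity needed is the share with earlier uptake among sites that both take up FMISO after TACE and progress. That share depends on how much hypoxia survives embolization, and Section 10.8 notes that necrotic tissue does not trap FMISO. The 50% figure shows only that hypoxia before TACE is a realistic possibility.

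**What to change.** In Sections 3.1, 3.3 and 6.1:

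- For patients 6-15, register the progression image to both the pre-TACE and the post-TACE FMISO PET-CT, and say so explicitly in Section 3.3.
- Tabulate each progression site descriptively as new (post only), persisting (both scans, with the direction of change in uptake), lost (pre only) or no uptake.
- Show patients 1-5 separately as post-TACE uptake with unknown pre-TACE status. List any later patient without a usable pre-TACE scan in the same way.
- State the limit: because hypoxia cycles and the pre-TACE scan may precede TACE by up to a week, new uptake suggests but does not prove TACE-induced hypoxia, and persisting uptake does not exclude it.
- Make clear that a technically adequate pre-TACE scan without tumor uptake is a valid negative. The example of a deficient scan in Section 3.5.2 could be read as removing it, which would empty the new class.

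The cost is a few sentences and one extra registration per paired patient, at most ten. No new scans, patients or radiation are needed. The downside is small counts in each class, so the table should stay descriptive.
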